### 6.4.4 Immediate Reporting of Adverse Events to the Sponsor-Investigator

### 6.4.4.1 Serious Adverse Events

Any serious adverse event, or follow up to a serious adverse event, including death due to any cause other than progression of the cancer under study that occurs to any subject from the time of start of treatment through 30 days following the last dose of study treatment, or the initiation of new anticancer therapy, whichever is earlier, whether or not related to pembrolizumab, must be reported within 24 hours to the Sponsor-Investigator. Additionally, after informed consent has been obtained, and prior to start of treatment, serious adverse events determined to be caused by a protocol-mandated intervention should also be reported.

Non-serious Events of Clinical Interest (See Section 6.4.4.2) will be forwarded to Sponsor-Investigator and will be handled in the same manner as SAEs.

Additionally, any serious adverse event, considered by an investigator who is a qualified physician to be related to Pembrolizumab that is brought to the attention of the investigator at any time outside of the time period specified in the previous paragraph also must be reported immediately to the Sponsor-Investigator.

All subjects with serious adverse events must be followed up for outcome.

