# 5.3.2.2 Dose Modifications of Other Treatments

## 5.3.2.3 Radiation Dose Modifications

Radiation treatment may be delayed due to toxicities for 1-7 consecutive days in patients in either treatment arm. Additionally, the start of brachytherapy can be delayed 1-14 days from completion of external beam RT if needed. All radiation treatments must be delivered within a total of 8 weeks, therefore treatment breaks should be kept to a minimum.

If radiation treatment is held, then cisplatin dose should be held until radiation treatment is resumed.

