## 5.7.1 Duration of Treatment

Subjects will continue to receive study treatment (defined as chemoradiation and pembrolizumab) until:

- Subject has completed all study treatments
- Disease progression
- Unacceptable adverse event(s)
- Subject withdraws consent for further treatment
- · Female subject has a confirmed positive serum pregnancy test
- Subject receives a non-study treatment (not protocol-specified) for their cancer
- Subject non-compliance
- General or specific changes in the subject's condition render the subject unacceptable for further treatment in the judgment of the investigator

If any of the above events occurs, the subject will be considered off treatment and in follow-up. Subjects will be followed for 5 years for PFS and OS, or until the trial is terminated per Section 5.7.4.

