#### 6.3.4.2.1 Tumor Samples

Tumor tissue samples must be collected at the intervals specified in the Trial Flow Chart, adhering to the following guidelines:

- 1. Pre-study Tissue sample: Fresh tissue must be collected from an office biopsy performed within the 4 weeks prior to start of treatment. If this biopsy yields insufficient tumor tissue, an archival sample may be requested.
- 2. CRT Treatment Sample: Fresh tissue must be collected during CRT treatment, at 5 ± 2 weeks. It is recommended that this sample be obtained at the time of brachytherapy delivery, so that biopsy can be performed conveniently.

Protocol/Amendment No.: UVA-LACC-PD201, Version 4.0, 06 March 2018

3. Treatment completion: Fresh tissue must be collected from an office biopsy performed at 12 weeks ± 10 days following completion of CRT.

Fresh tumor tissue should be divided into portions for several preparations including formalin fixed paraffin embedded (FFPE) in blocks, flash freezing and single cell isolations. Detail instructions for tissue processing and shipping will be provided in a separate study manual.

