#### 6.4 Assessing and Recording Adverse Events

Adverse events should be collected from the start of treatment through a minimum of 30 days following the last study treatment.

After informed consent has been obtained, and prior to initiation of investigational treatment, only serious adverse events caused by a protocol-mandated intervention should be reported (e.g., serious adverse events related to invasive procedures such as biopsies).

**After initiation of study treatment**, all adverse events will be reported according to the guidelines in the following sections. Throughout the study, investigators should report any deaths, serious adverse events, or other adverse events of concern that are believed to be related to the investigational intervention.

An adverse event is defined as any untoward medical occurrence in a patient or clinical investigation subject administered a pharmaceutical product and which does not necessarily have to have a causal relationship with this treatment. An adverse event can therefore be any unfavorable and unintended sign (including an abnormal laboratory finding, for example), symptom, or disease temporally associated with the use of a medicinal product or protocol-specified procedure, whether or not considered related to the medicinal product or protocol-specified procedure. Any worsening (i.e., any clinically significant adverse change in frequency and/or intensity) of a preexisting condition that is temporally associated with the use of pembrolizumab, is also an adverse event.

Adverse events may occur during the course of the use of Pembrolizumab in clinical trials or within the follow-up period specified by the protocol, or prescribed in clinical practice, from overdose (whether accidental or intentional), from abuse and from withdrawal.

Table 6. Adverse Event Reporting Overview						
Event Type	Collection Timeframe	Reporting Timeframe	Reference			
Routine Adverse Events	the start of treatment through at	Within 30 days to UVa	Section 6.4			
Serious Adverse Events†	least 30 days following the last study treatment	Within 24h to UVa	Section 6.4.4.1			
Events of Clinical Interest	the start of treatment through 90 days following the last dose of pembrolizumab (or date subject starts new cancer treatment)	Within 24h to UVa	Section 6.4.4.2			
Overdose	On pembrolizumab dosing days	Within 24h to UVa	Section 6.4.2			

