## 6.4.1.3 Attribution

The Principal Investigator will evaluate all AEs and assess their toxicity and attribution, if any, to pembrolizumab. See Table 8 for further guidance on evaluation of attribute. The following criteria will define the attribution:

**Definite:** The AE is clearly related to the investigational intervention. **Probable:** The AE is likely related to the investigational intervention. **Possible:** The AE may be related to the investigational intervention. **Unlikely**: The AE is doubtfully related to the investigational intervention. **Unrelated**: The AE is NOT related to the investigational intervention.

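### Sponsor reporting of serious complications from the mandated 12-week post-CRT biopsy is not required in on-schedule Arm 2 patients or in part of Arm 1

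*Combined protocol and SAP*

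**What the plan says.** **The biopsies.** Section 6.3.4.2.1 requires three tissue samples in both arms. Two come after treatment has started. For the first, "Fresh tissue must be collected during CRT treatment, at 5 ± 2 weeks". For the last, "Fresh tissue must be collected from an office biopsy performed at 12 weeks ± 10 days following completion of CRT". Section 6.3.4.2 sends the tissue to the coordinating university for analysis and storage for research.

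**The SAE window.** Section 6.4.4.1 has SAEs reported within 24 hours, whether or not related to pembrolizumab, "from the time of start of treatment through 30 days following the last dose of study treatment", or until new anticancer therapy if that comes first. Section 5.7.1 fixes the term: "study treatment (defined as chemoradiation and pembrolizumab". The clock therefore runs from the later of the two, and a biopsy does not restart it.

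**After the window.** Section 6.4.4.1 then requires only SAEs that a physician investigator considers related to pembrolizumab. Section 6.4 has a rule for the whole study, but it is tied to the investigational intervention. Section 6.4.1.3 uses that same term to grade attribution, where the task is to "assess their toxicity and attribution, if any, to pembrolizumab".

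**Before treatment.** Between consent and start of treatment, Sections 6.4 and 6.4.4.1 make SAEs caused by a protocol-mandated intervention reportable. Section 6.4 gives as its example "serious adverse events related to invasive procedures such as biopsies".

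**General AE collection.** Section 6.4 states a floor: "Adverse events should be collected from the start of treatment through a minimum of 30 days following the last study treatment". Table 6 repeats it as at least 30 days, for routine AEs and SAEs alike.

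**The concern.** The protocol accepts that its own biopsies can cause serious harm and has a reporting clause for that harm, but the clause stops when treatment starts. During treatment the all-cause window takes over. Once that closes, nothing replaces it, although one compulsory biopsy, of irradiated cervix, is still to come.

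A bleed or infection after that biopsy that led to admission would be an adverse event under the Section 6.4 definition, which includes events associated with a protocol-specified procedure. If it fell after the 30-day limit and was not attributed to pembrolizumab, Section 6.4.4.1 would not require the site to report it to the sponsor-investigator. The attribution scale has no category in which to record the biopsy as the cause. The flow charts for both arms also leave the adverse-event review row blank in the 12-week imaging column, where the biopsy is scheduled.

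Safety is a primary objective (Section 3.1), and the DSMC is to review all adverse events (Section 6.4.5.1). It can review only what reaches it. At stake is oversight of a compulsory research procedure, with required capture that also differs between arms.

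**Working it through.** The check is calendar arithmetic, with day 1 as the start of treatment.

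**Inputs**
- Arm 1 pembrolizumab: three doses every 21 days from week 9 (Section 6.1.1), so days 57, 78 and 99.
- Arm 2 pembrolizumab: three doses every 21 days from day 1 (Section 6.1.2), so days 1, 22 and 43.
- Latest CRT end: day 56, since "All radiation treatments must be delivered within a total of 8 weeks" (Section 5.3.2.3).
- Earliest CRT end: day 33. This is an assumption: 25 weekday fractions at the short end of the 5-8 week interval in Table 2. It is early, because brachytherapy must be fitted in as well.
- Window close = max(CRT end, last pembrolizumab) + 30.
- Biopsy = CRT end + 84 ± 10, that is CRT end + 74 to + 94.

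**Reproducing the flow chart.** Week = floor((day − 1)/7) + 1. Days 57, 78 and 99 give weeks 9, 12 and 15, matching the stated W9-W15. Days 1, 22 and 43 give weeks 1, 4 and 7, within the stated W1-W9.

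**Arm 2**
- CRT ends on days 43-56: the window closes at CRT end + 30. The biopsy is 74 − 30 = 44 to 94 − 30 = 64 days late.
- CRT ends on day 33, last dose on day 43: the window closes on day 73 and the biopsy falls on days 107-127, which is 34 to 54 days late.
- Most extreme on-schedule case, CRT ending on day 33 and the last dose at the end of week 9 (day 63): the window closes on day 93. The earliest biopsy, day 107, is 14 days late.
- General condition: the earliest biopsy is inside only if last dose + 30 ≥ CRT end + 74, so the last dose must come at least 44 days after CRT ends. The largest on-schedule gap is 63 − 33 = 30 days. Every on-schedule Arm 2 biopsy is outside.

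**Arm 1, nominal schedule** (last dose day 99, window closes day 129)

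| CRT ends | Biopsy days (nominal) | Position relative to day 129 |
|---|---|---|
| 35 | 109-129 (119) | all inside |
| 42 | 116-136 (126) | 13 days inside to 7 outside; nominal has 3 days of cover |
| 49 | 123-143 (133) | 6 days inside to 14 outside; nominal 4 outside |
| 56 | 130-150 (140) | 1 to 21 days outside |

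The nominal biopsy is inside when CRT end + 84 ≤ 129, that is, when CRT ends by day 45. It is outside for days 46-56.

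**Arm 1, other schedules**
- Third dose skipped: last dose day 78, window closes day 108. The nominal biopsy is inside only if CRT ends by day 24, so it is outside for every CRT end from day 33 to day 56.
- Two 7-day delays plus the 3-day allowance: last dose 99 + 14 + 3 = day 116, window closes day 146. The nominal biopsy is inside if CRT ends by day 62, so it is inside for all.

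**During-CRT biopsy.** It is taken while CRT continues, and the window cannot close before CRT end + 30, so it is covered in both arms.

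**The case against.** A reader might infer that harm from biopsying irradiated cervix is never captured. The documents do not support that:
- The during-CRT biopsy is also of irradiated cervix and lies inside the all-cause window.
- Some Arm 1 12-week biopsies are inside too.
- Section 6.4 and Table 6 set 30 days as a minimum, so a site may collect for longer.
- Section 6.4.1 has all adverse events entered in the medical record.
- Section 6.4.4.3 wants Grade 3 to 5 events in the database even when unrelated or unlikely related, and states no window of its own.
- Section 6.4.4.4 sends serious, unexpected events to the site IRB with no pembrolizumab test.

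These points stand, but they do not close the gap. A minimum lets a site stop at 30 days and comply, while Section 6.4.4.1 gives a fixed end. The database rule presumably inherits the collection window. The IRB route follows local policy and depends on the event being judged unexpected. The AE definition says what counts as an event, not how long to collect it.

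A reader might also infer that many Arm 1 patients are affected. The documents give no distribution of CRT duration, so no share can be stated.

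Two further objections limit the weight of the point. The gap leaves the DLT stopping rule (first 30 days after the first infusion), the immunologic endpoints and the futility rule untouched. Unequal capture between arms matters less in a trial that Section 7.0 says is not meant for definitive comparison of arms. Both are fair. No biopsy complication rate is given, so the number of missed events cannot be estimated.

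**Conclusion.** The concern holds as a gap in required sponsor reporting, not as a total absence of capture. Serious complications of the 12-week biopsy that are not attributed to pembrolizumab need not be reported to the sponsor-investigator in any on-schedule Arm 2 patient. The same is true in Arm 1 when the biopsy falls after the window closes, which on the nominal schedule means CRT ending on days 46-56 for a biopsy at exactly 12 weeks. An in-window Arm 1 biopsy may still have only a few days of cover.

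The Arm 2 margin of 44 to 64 days rests on CRT ending on or after about day 43; the minimum of 14 days rests on CRT ending no earlier than day 33 and all doses falling within the flow-chart weeks. Patients who abandon CRT or depart from schedule are not covered by these figures. The change is worth making because the protocol already has the principle and applies it only before treatment.

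**What to change.** In Section 6.4, Table 6 and Section 6.4.4.1, extend the existing pre-treatment clause so that SAEs judged to be caused by a protocol-mandated procedure are reportable from consent through 30 days after the last protocol-mandated biopsy. That runs to CRT end + 104 to + 124 days (74 + 30 to 94 + 30; nominal + 114). On the nominal schedules the present window closes at CRT end + 30 to + 40 in Arm 2 and + 73 to + 96 in Arm 1.

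In Section 6.4.1.3, add protocol-mandated procedure as an attribution category alongside pembrolizumab.

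A brief telephone contact after the biopsy can be used to apply the rule. An adverse-event review on the biopsy day alone could catch an immediate bleed but not a delayed complication.

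The cost is protocol and CRF wording and minor follow-up work. Treatment, clinic visits, samples and sample size do not change.

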## 6.4.4.2 Events of Clinical Interest

Selected non-serious and serious adverse events are also known as Events of Clinical Interest (ECI) and must be recorded as such on the Adverse Event case report forms/worksheets and reported within 24 hours to the Sponsor-Investigator using the Safety Reporting Form.

Events of clinical interest for this trial include:

1. an overdose of Pembrolizumab, as defined in Section 6.4.2 - Definition of an Overdose for This Protocol and Reporting of Overdose to the Sponsor-Investigator, that is not associated with clinical symptoms or abnormal laboratory results.

2. an elevated AST or ALT lab value that is greater than or equal to 3X the upper limit of normal and an elevated total bilirubin lab value that is greater than or equal to 2X the upper limit of normal and, at the same time, an alkaline phosphatase lab value that is less than 2X the upper limit of normal, as determined by way of protocol-specified laboratory testing or unscheduled laboratory testing.\*

\*Note: These criteria are based upon available regulatory guidance documents. The purpose of the criteria is to specify a threshold of abnormal hepatic tests that may require an additional evaluation for an underlying etiology. The trial site guidance for assessment and follow up of these criteria can be found in the Investigator Trial File Binder (or equivalent).

#### 3. Additional adverse events:

A separate guidance document has been provided titled "Event of Clinical Interest Guidance Document" (previously entitled, "Event of Clinical Interest and Immune-Related Adverse Event Guidance Document"). This document provides guidance regarding identification, evaluation and management of ECIs and irAEs.

ECIs (both non-serious and serious adverse events) identified in this guidance document from the date of first dose through 90 days following cessation of treatment, or 30 days after the initiation of a new anticancer therapy, whichever is earlier, need to be reported within 24 hours to the Sponsor-Investigator using the Safety Reporting Form.

Subjects should be assessed for possible ECIs prior to each dose. Lab results should be evaluated and subjects should be asked for signs and symptoms suggestive of an immune-related event. Subjects who develop an ECI thought to be immune-related should have additional testing to rule out other etiologic causes. If lab results or symptoms indicate a possible immune-related ECI, then additional testing should be performed to rule out other etiologic causes. If no other cause is found, then it is assumed to be immune-related.

# Table 7. Evaluating Adverse Events

V4.0 CTCAE Grading	Grade 1	Mild; asymptomatic or mid symptoms; clinical or diagnostic observations only; intervention not indicated.						
J	Grade 2	Moderate; minimal, local or noninvasive intervention indicated; limiting age-appropriate instrumental ADL.						
	Grade 3 Severe or medically significant but not immediately life-threatening; hospitalization or prolongation or hospitalization indicated; disabling; limiting self-care ADL.							
	Grade 4	Life threatening consequences; urgent intervention indicated.						
	Grade 5 Death related to AE							
Seriousness	A serious adverse	event is any adverse event occurring at any dose or during any use of Merck product that:						
	The sults in death: or							
	†Is life threatening; or places the subject, in the view of the investigator, at immediate risk of death from the event as it occurred (Note: This does not include an adverse event that, had it occurred in a more severe form, might have caused death.); or							
	†Results in a persistent or significant disability/incapacity (substantial disruption of one's ability to conduct normal life functions); or							
	†Results in or prolongs an existing inpatient hospitalization (hospitalization is defined as an inpatient admission, regardless of length of stay, even if the hospitalization is a precautionary measure for continued observation. (Note: Hospitalization [including hospitalization for an elective procedure] for a preexisting condition which has not worsened does not constitute a serious adverse event.); or							
	†Is a congenital anomaly/birth defect (in offspring of subject taking the product regardless of time to diagnosis);or							
	Is a new cancer; (that is not a condition of the study) or							
	Is an overdose (whether accidental or intentional). Any adverse event associated with an overdose is considered a serious adverse event. An overdose that is not associated with an adverse event is considered a non-serious event of clinical interest and must be reported within 24 hours.							
	Other important medical events that may not result in death, not be life threatening, or not require hospitalization may be considered a serious adverse event when, based upon appropriate medical judgment, the event may jeopardize the subject and may require medical or surgical intervention to prevent one of the outcomes listed previously (designated above by a †).							
Duration		nd stop dates of the adverse event. If less than 1 day, indicate the appropriate length of time and units						
Action taken		vent cause the Merck product to be discontinued?						
Expectedness	Events included in Pembrolizumab Investigator's Brochure should be considered expected with pembrolizumab treatment for the purposes of assessment for expedited reporting requirements.							
Relationship to test drug	Did the Merck product cause the adverse event? The determination of the likelihood that the Merck product caused the adverse event will be provided by an investigator who is a qualified physician. The investigator's signed/dated initials on the source document or worksheet that supports the causality noted on the AE form, ensures that a medically qualified assessment of causality was done. This initialed document must be retained for the required regulatory time frame. The criteria below are intended as reference guidelines to assist the investigator in assessing the likelihood of a relationship between the test drug and the adverse event based upon the available information.							
	The following components are to be used to assess the relationship between the Merck product and the AE; the greater the correlation with the							
	components and their respective elements (in number and/or intensity), the more likely the Merck product caused the adverse event (AE):							
	Exposure	Is there evidence that the subject was actually exposed to the Merck product such as: reliable history, acceptable compliance assessment (pill count, diary, etc.), expected pharmacologic effect, or measurement of drug/metabolite in bodily specimen?						
	Time Course	Did the AE follow in a reasonable temporal sequence from administration of the Merck product? Is the time of onset of the AE compatible with a drug-induced effect (applies to trials with investigational medicinal product)?						
	Likely Cause	Is the AE not reasonably explained by another etiology such as underlying disease, other drug(s)/vaccine(s), or other host or environmental factors						

### Protocol/Amendment No.: UVA-LACC-PD201, Version 4.0, 06 March 2018

Relationship	The following co	omponents are to be used to assess the relationship between the test drug and the AE: (continued)						
to Merck	Dechallenge	Was the Merck product discontinued or dose/exposure/frequency reduced?						
product		If yes, did the AE resolve or improve?						
(continued)		If yes, this is a positive dechallenge. If no, this is a negative dechallenge.						
		(Note: This criterion is not applicable if: (1) the AE resulted in death or permanent disability; (2) the AE resolved/improved despite						
		continuation of the Merck product; or (3) the trial is a single-dose drug trial); or (4) Merck product(s) is/are only used one time.)						
	Rechallenge	Was the subject re-exposed to the Merck product in this study?						
		If yes, did the AE recur or worsen?						
		If yes, this is a positive rechallenge. If no, this is a negative rechallenge.						
		(Note: This criterion is not applicable if: (1) the initial AE resulted in death or permanent disability, or (2) the trial is a single-dose drug trial);						
		or (3) Merck product(s) is/are used only one time).						
		NOTE: IF A RECHALLENGE IS PLANNED FOR AN ADVERSE EVENT WHICH WAS SERIOUS AND WHICH MAY HAVE BEEN						
		CAUSED BY THE MERCK PRODUCT, OR IF REEXPOSURE TO THE MERCK PRODUCT POSES ADDITIONAL POTENTIAL						
		SIGNIFICANT RISK TO THE SUBJECT, THEN THE RECHALLENGE MUST BE APPROVED IN ADVANCE BY THE U.S. CLINICAL						
		MONITOR AS PER DOSE MODIFICATION GUIDELINES IN THE PROTOCOL.						
	Consistency	Is the clinical/pathological presentation of the AE consistent with previous knowledge regarding the Merck product or drug class pharmacology						
	with Trial	or toxicology?						
	Treatment							
	Profile							

